
The study team will strictly adhere to the procedures detailed in this protocol, including methods to mitigate risks to participants.

Justification of procedures

Because this study involves no more than minimal risks to participants, the above described procedures and data collection techniques are justified as they are all necessary to satisfy the research aims of this study. Additionally, having the option to complete visits virtually or in-person will ensure maximum safety for patients and providers in times of COVID-19 surges.

E. Potential Scientific Problems

As attrition may be a concern in hard to reach populations,⁶⁹ we accounted for 22% attrition in our sample size calculations. To encourage retention, as was successful in the K99 trial in the DR, participants will be reminded of visits via phone calls prior to study visits and incentives appropriate for each site will be provided. Recruitment will be monitored to ensure a sufficient pace of enrollment and timelines will be extended if needed.

Intervention fidelity and contamination are concerns as participants may be scheduled to see the incorrect provider, providers may use infographics with control group participants, or simply may not use infographics. Intervention fidelity will be assessed by providers, patients, and a study team member, and contamination addressed with intent-to-treat analysis.

F. Data Analysis Plan

Sample size calculations

Individual interviews

Up to 15 participants will participate in individual interviews. This sample size was established as 15 participants are likely to be able to identify 90% of usability concerns in informatics-based studies⁷⁰ and as few as 10 are likely to achieve saturation in qualitative studies on specific themes (e.g. the experience of living with HIV) with relatively homogenous samples (e.g. Latino persons of predominantly Mexican origin/descent living in Denver, CO).⁷¹

RCT – Interventionists

Up to 5 interventionists at each site will be purposefully selected to participate. This sample size is based on preliminary feasibility studies.

RCT – patient participants (n=164, 82 at each site, 41 per group)

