To establish sample size for the RCT, we used a longitudinal power analysis approach for testing the “time averaged difference” in two group means for a continuous outcome over time.⁷² This effect size is analogous to Cohen’s D: $(\mu_1 - \mu_2)/\sigma$, where μ_1, μ_2 are the outcome means (averaged over time) in the treatment and control groups, and σ is the standard deviation of the outcome (assumed constant over time and equal for both groups).⁷³ Assuming a slightly less than “medium” effect size of D=0.45,⁷³ 80% power, and two-sided significance level $\alpha=0.05$, the required total sample size ranges from 68-126 depending on the assumed constant pairwise correlation between the 4 repeated measures (which we varied from 0.25 to 0.75) (Table 3). We conservatively assume a correlation of 0.75 which requires a total sample size of 126. To account for 22% attrition, higher than our attrition rate that we experienced in the pilot tests in the Dominican Republic (16%) to account for complications with this hard to reach population of Denver, we increased the sample size to 164 (161.5 rounded up to ensure equal numbers in each group).

Interviews with key stakeholders

Up to 15 interviews with key stakeholders will be conducted at each site (CO and DR). This is based on estimates that 12 interviews per site can lead to saturation of identified themes.^{74,75}

Summary of total sample size per site:

DR total # of participants to be consented to achieve study aims: 100 (maximum recruitment at this site will be 115 to account for failures and withdrawals).

Denver Health total # of participants to be consented to achieve study aims: 121 (maximum recruitment at this site will be 140 to account for failures and withdrawals).

Analytic plan for each study aim

Aim 1: See individual interviews in section C above.

Aim 2: *Conduct a multi-site randomized controlled trial to assess the efficacy of the intervention (infographics administered through a mobile app) as compared to standard care in improving treatment outcomes (CD4 count, viral load, self-efficacy to manage HIV, among others) of PWH and determine how resultant effects vary over time (baseline to 9-months) and between sites (US and CO).*

Table 3. Necessary sample size for testing the time-averaged difference between two groups of equal size				Primary	
		ρ (constant correlation of 4 repeated measures over time)			

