Effect Size (Average diff. in 2 group means over time, analogous to Cohen's D: $(\mu_1 - \mu_2)/\sigma$)		0.25	0.50	0.75	
0.20 (Small)		344	491	638	
0.35		113	161	209	
0.40		86	123	160	
0.45		68	97	126	
0.50 (Medium)		55	79	103	
0.80 (Large)		22	31	40	

Note: Calculations with 80% power and $\alpha=0.05$ with 4 repeated measures assuming exchangeable/ constant pairwise correlation " ρ " varied from 0.25 to 0.75.

Analysis: A linear mixed effect model (LMM) will be used to compare the effects of the two groups (treatment vs. standard of care) on the primary longitudinal outcome of CD4 count between baseline and the three follow up visit time points (3-, 6-, and 9-months). Subject-specific random intercepts and slopes will be used to model heterogeneity in the subjects' trajectories. Three primary tests will be considered: 1) testing the time-averaged difference in the outcome between the two treatment groups (main effect for treatment), and 2) test whether change-over-time differs between the two treatment groups (treatment*time interaction), and 3) test whether the treatment effect differs between the two sites (treatment*site interaction and treatment*site*time interaction).

Secondary Analyses: The same analysis plan will be repeated with the remaining longitudinal outcomes Table 2 of the Research Strategy section of this application. Linear mixed effect models (LMM) will be used for continuous outcomes (CD4 count, viral load, knowledge questions, engagement with health care provider scale, satisfaction with care,

self-efficacy, health related quality of life PROMIS-29), logistic generalized linear mixed effect model (GLMM) will be used for the dichotomous adherence score (SMAQ-6), and ordinal GLMM will be used for the health status assessment score while LMM will be used for the additional health status continuous score. Lastly, as a simpler alternative to longitudinal mixed effect models (that use all time points), standard general linear models will be used to model outcomes at 9 months adjusting for baseline, thus testing whether an outcome differs between the two interventions at 9 months.

The System Usability Scale (SUS) that providers complete during the second training session will be scored according to published guidelines.⁷⁶

D.9.4. Aim 3: Assess implementation factors of integrating the SMART on FHIR app into EHRs through in-depth interviews and leverage findings to ensure the app effectively interfaces with EHRs in the CO and the DR.

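### The only named test of the 9-month effect is a baseline-adjusted general linear model that fits neither the binary nor the ordinal outcome and discards interim data from anyone missing the 9-month value

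*Combined protocol and SAP*

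**What the plan says.** Section IV.F (Data Analysis Plan, Aim 2) plans a linear mixed model for CD4 count over baseline, 3, 6 and 9 months, with random intercepts and slopes. The tests listed are the time-averaged treatment difference, the treatment-by-time interaction, and the interactions of treatment with site and with site and time. No contrast at 9 months is listed, and the coding of time (linear or categorical) is not stated.

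The Secondary Analyses paragraph repeats this plan for the other outcomes. Linear mixed models serve the continuous outcomes. A logistic GLMM "will be used for the dichotomous adherence score (SMAQ-6), and ordinal GLMM will be used for the health status assessment score". The paragraph closes with a simpler alternative to the mixed models: "standard general linear models will be used to model outcomes at 9 months adjusting for baseline", to test for a difference between the arms at 9 months.

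Two other places bear on this. Under RCT study procedures (Section IV.C), the intervention is withheld at the 9-month visit so that longer-term effects can be assessed. Table 2 agrees: exposure at baseline, 3 and 6 months, and assessment only at 9 months. On dropout, Potential Scientific Problems says "we accounted for 22% attrition in our sample size calculations". No method for missing outcomes is given, and intent-to-treat is mentioned only as the answer to contamination.

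**The concern.** The 9-month visit is the trial's only look at the effect after exposure has stopped, and one loosely specified sentence carries that comparison. Two things are unsettled.

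**Outcome type.** The same paragraph treats SMAQ-6 as binary and the health status assessment as ordinal, then names one normal-error model for 9-month outcomes without restriction. Read literally, those two scores get a linear model. Read charitably, they have no 9-month model at all. Either way the choice is left to the analyst.

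**Missing data.** A model of the single 9-month value given baseline ignores the 3- and 6-month data of anyone who lacks that value. Without imputation it is valid if missingness depends only on arm and baseline. A likelihood-based mixed model also allows missingness to depend on the observed 3- and 6-month values. The simpler alternative therefore needs the stronger assumption, in a population where the plan itself expects attrition. If people doing badly at 6 months leave, and do so differently by arm, the 9-month estimate is biased.

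**Working it through.** **Inputs from the plan.** "80% power, and two-sided significance level" of 0.05; "effect size of D=0.45"; "We conservatively assume a correlation of 0.75 which requires a total sample size of 126"; Table 3 is calculated "with 4 repeated measures assuming exchangeable/ constant pairwise correlation"; 22% attrition; 164 randomised, 82 per arm. Dropout timing and mechanism are not in the documents and are assumed below.

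**1. The plan's own figure.** For a time-averaged difference with m = 4 measures,

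N = 4(z₀.₉₇₅ + z₀.₈₀)² [1 + (m − 1)ρ] / (m D²) = 4 × (1.960 + 0.842)² × 3.25 / (4 × 0.45²) = 126.0.

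Then 126 / 0.78 = 161.5, raised to 164. All 18 cells of Table 3 reproduce to within rounding. The sample size is not in question here.

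**2. Who leaves the 9-month model.** 164 × 0.22 = 36.1, so about 36 are excluded and 128 remain. This treats attrition as a missing 9-month value. CD4 and viral load are taken from medical records (Sections IV.A and D.2.1), so fewer may be missing for those two.

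**3. Precision.** In SD units, the standard error of the baseline-adjusted 9-month difference is sqrt[2(1 − ρ²) / (82 × 0.78)]. At ρ = 0.75 this is sqrt(0.875 / 63.96) = 0.117. The comparator is a repeated-measures model using all visits, with visit categorical, a common baseline mean and exchangeable correlation. The range runs from all dropout before 3 months to all dropout after 6 months. Power assumes that the 9-month difference is also 0.45.

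| ρ | Variance, single-visit / all-data | Power, single-visit | Power, all-data |
|---|---|---|---|
| 0.25 | 1.00 to 1.015 | 74.8% | 74.8 to 75.4% |
| 0.50 | 1.00 to 1.04 | 83.6% | 83.6 to 84.9% |
| 0.75 | 1.00 to 1.06 | 97.0% | 97.0 to 97.7% |

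A separate simulation of 600 trials per scenario (82 per arm, ρ = 0.75) gave variance ratios of 1.02 under random dropout and 1.085 under value-dependent dropout in controls. The loss of precision is small throughout.

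**4. Bias.** True difference 0.45 at every follow-up visit, 22% dropout after 6 months, 400,000 simulated participants per arm, ρ from 0.25 to 0.75. Where dropout depends on the outcome, its log-odds fall by 1 per SD of the 6-month value.

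| Assumed dropout | Single-visit estimate | Bias |
|---|---|---|
| Random (600-trial simulation, ρ = 0.75) | 0.448 | nil, all-data also 0.448 |
| Same slope in both arms, each arm set to 22% | 0.45 | nil |
| One shared rule, about 25% control and 19% treatment dropout | 0.437 to 0.442 | 2 to 3% |
| Controls only, random in the treatment arm | 0.398 to 0.418 | 7 to 12% |

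The second row follows by symmetry: each arm loses the same part of its own distribution, so the difference is preserved. The percentages are, for example, (0.45 − 0.398) / 0.45 = 11.6% and (0.45 − 0.442) / 0.45 = 1.8%. In the last two rows the all-data estimate stays between 0.447 and 0.453. The 600-trial simulation of the controls-only case gave 0.413 against 0.449 for the all-data estimate.

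**The case against.** The analysis is explicitly secondary and offered as a simpler alternative. The primary CD4 model and the main secondary models use every visit and are untouched. A baseline-adjusted endpoint comparison beside a mixed model is common practice. The largest bias comes from outcome-dependent dropout in one arm only, for which the documents give no basis. Even then, the shift in the 600-trial run (0.45 − 0.413 = 0.037) is about 0.3 of the standard error of 0.117, and it is toward the null. A linear model of a randomised binary outcome also estimates a risk difference, which can be interpreted with suitable standard errors. All of this stands and limits the weight of the point.

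It does not remove the point. The plan does not say that a risk difference is intended, and that argument does not extend to the ordinal score. Calling the model secondary does not supply another test of the 9-month effect, because none of the listed mixed-model tests isolates that visit.

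Three stronger readings are tempting, and the documents do not support them:

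- **A reader might infer that the plan decides to fit linear models to all outcomes, binary and ordinal included.** The sentence is unrestricted but does not say so. The supportable finding is that no suitable 9-month model is named for those two.
- **A reader might infer a completers-only analysis.** The plan does not say that either. Only a missing baseline or 9-month value excludes someone; a missed 3- or 6-month visit does not.
- **A reader might infer that the planned mixed models already give this contrast, so the simple model is redundant.** No 9-month contrast is listed and time coding is unstated. If time is linear, a 9-month contrast would rest on the fitted trend.

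**Conclusion.** The point holds as a modest one about a secondary analysis. The 9-month comparison rests on a single model that is not matched to two of the outcome types and that leaves available interim data unused. A better method is at hand in models of the kind already planned.

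About 36 of 164 would be excluded if the planned attrition means missing 9-month values. Bias runs from nil to about 3% unless outcome-dependent dropout differs by arm; in the controls-only case it is about 7 to 12% toward the null. The gain in precision from using all visits is slight and would not justify the change by itself. These sizes depend on an assumed dropout rule, late dropout, exchangeable correlation and a continuous outcome. No size has been put on the mismatch for SMAQ-6 and health status; that part rests on the text alone.

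**What to change.** Pre-specify the 9-month treatment contrast from the mixed models: time as categorical, a common baseline mean across arms (justified by randomisation), and site, the stratification factor, as a fixed effect. Use the linear mixed model for continuous outcomes, the logistic GLMM for SMAQ-6 and the ordinal GLMM for health status.

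Keep the single-visit model only as a sensitivity check, adjusted for baseline and site, with logistic regression for SMAQ-6 and proportional-odds regression for health status. State how missing 9-month values are handled in it. Note that its odds ratios are marginal over subjects while those from the GLMMs are subject-specific, so the two need not agree numerically.

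The cost is a few lines in the analysis plan and a contrast to be added to the planned models. No extra data are needed and the sample size does not change.

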Results from the first K99 feasibility study, conducted with a validated methodology in the DR, demonstrate that using infographics to improve clinician-patient communication and health outcomes is feasible and acceptable. Qualitative responses from clinicians who administered the intervention were overwhelmingly supportive of not only continuing to use the intervention, but indicated infographics should be further developed to encompass more topics and be made available outside of the study, to other providers at the clinic. Statistically significant changes were observed in the primary outcome measure (CD4 count) of patient participants between baseline and 9-month visits. As several other outcome measures (viral load, engagement with clinician, HIV-related knowledge) showed statistically significant improvements over this time period as well, it is likely the intervention had a positive effect on these individuals. As with all studies, there were limitations. First, all participants were recruited from one health clinic in the Dominican Republic so results may not be generalizable. The second feasibility trial, recently completed in NY, will provide further evidence of feasibility and usability among a similar population in a different clinical context. Another main limitation of both feasibility studies is that there was not a control group, so from current data we are unable to establish how much of the improvement seen in the Dominican cohort was due to infographics and what was attributable to confounders. When larger cohorts are randomized to the treatment and control groups in the planned multi-site trial during the R00 phase, it will be possible to compare results of participants who received the intervention to those who did not, which will provide further evidence of the actual treatment effect.

IV. Research Methods

A. Outcome Measure(s): Outcomes were selected using a conceptual model depicting distinct pathways through which clinician-patient communication can influence health outcomes.⁵⁷ In this model, outcomes that are affected by clinician-patient communication are separated into three distinct categories, proximal, intermediate, and long-term. Table 1 summarizes the corresponding outcome measures and the scale or type of data that will be collected for each.

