Information recall	Questions pertaining to final infographic content
Engagement with clinician	Engagement with Health Care providers Scale ^{*48}
Satisfaction with care	1. Two questions assessing satisfaction ^{*49} 2. CHAPS Survey 2.0 ^{*50}
Intermediate Outcomes	
Self-efficacy to manage HIV	Self-efficacy to manage chronic conditions scale ^{*51}
Adherence	1. SMAQ 6 item scale ^{*52} 2. Medication possession ratio (MPR) ^{*53,54}
Long-term Outcomes	
Health related quality of life	PROMIS 29 ^{*55}
Health status	1. CD4 count and viral load 2. Health Status Assessment ^{*56}

Note: * scale validated in Spanish

Participants will be employees of the research site in the Dominican Republic who are Spanish/Creole bilingual and provide HIV-related health information to patients in Creole.

Validation of infographics with non-Latino PWH

Inclusion criteria for this phase of the study will be 1) Does not identify as Hispanic/Latino 2) Identifies as White or Black race 3) Has HIV infection, confirmed in electronic health record 4) (\geq 18 years) of age.

C. Study Design and Research Methods

Study Design

This will be a mixed-methods study with several components:

- 1) Individual interviews (Aim 1)
- 2) Multi-site randomized controlled trial (RCT) (Aim 2)
- 3) In-depth individual interviews with Key stakeholders (Aim 3)
- 4) In-depth interviews with patient participants from the RCT (Aim 4)
- 5) Interviews with non-Latino PWH (additional component of study added 09/20/23)

Study Settings

The trial will take place at two outpatient clinics specializing in HIV treatment. The US site will be CPH, in Denver, CO and the Dominican site is Clínica de Familia La Romana (CFLR). These are the ideal clinical locations for this trial because they offer services to two large, distinct Latino populations who are the target of this intervention (Mexican and Dominican PWH). Including a site in the US and one in the DR will also further augment intervention generalizability. Additionally, the EHR infrastructures at these sites are ideal for further development of the SMART on FHIR app, which will enable scalability to sites across the US and abroad. CPH in CO uses EPIC as their EHR and CFLR uses the open-source EHR, Odoo. Both systems can interface with SMART apps,⁵⁸ and their administrative structures permit app integration with EHRs.

Individual interviews to adapt infographics to Colorado context

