Intervention infographics are available in English and in Spanish and were created using a rigorous iterative design process.⁴⁶ They are intended to assist clinicians deliver patient education through culturally appropriate and visually appealing representations of key HIV-related concepts, systematically identified in a preliminary study.⁴⁷ For the trial, up to five clinicians at each site will be selected to use infographics. These “interventionists” will first attend a training, held by the study team, on how to use infographics to guide education using motivational interviewing (MI),³⁰ the mobile health application that contains the infographics, and on how to maintain intervention fidelity.^{59,60} During training, key concepts of infographics and MI will be reviewed then attendees will conduct “mock visits” to review learned components of MI, the mobile application and infographic content, confirm understanding of study procedures, and ensure interventionists uniformly administer the intervention. Additional training sessions will be held during the study to reinforce interventionists’ ability to implement learned skills. Also, during the second training session, interventionists will complete a questionnaire (the system usability scale (SUS)) to assess usability of the mobile health app containing infographics. During the study, in normal clinic visits, interventionists will use MI and infographics to guide education with participants using the infographics that will appear in the app, easily accessible on iPads. If a provider is conducting a telehealth visit with a study participant in the treatment group, during times of COVID-19 surges or for any other reason, they will have paper copies of the infographics to show participants during video visits.

RCT study procedures

During recruitment, clinic staff at each site will work closely with the Research Assistants (RA) to identify eligible participants on or before each recruitment day by verifying eligibility criteria in the electronic health records (EHR).

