At the DR site, the RA will notify clinic staff of eligible participants at the beginning of each recruitment day. Then, when an eligible participant presents to the clinic for their regularly scheduled appointment, initial contact will be made by clinic staff (face to face) who will introduce the study by providing a brief description of the study using the approved recruitment script and will then introduce interested participants to the RA, who will further explain the study, confirm eligibility, and complete informed consent and randomization.

At the US site, the RA will identify eligible participants for recruitment days the day before. Then, the RA will call eligible participants to confirm eligibility and explain the study by providing a brief description using the approved recruitment script. If a potential participant is interested, they will be invited to come to the clinic an hour before their scheduled appointment to complete the study visit. When a participant presents to the clinic, the RA will further explain the study, confirm eligibility, and complete informed consent and randomization. If the baseline/enrollment visit will be completed virtually, the procedures for recruitment/enrollment will be exactly the same, they will just be conducted over the phone

Table 2. Study activities at each visit in the RCT

Time point	Activity and group (Treatment (Tx), Control (Cl), or Both)
Baseline	
• Randomization• Baseline assessment (Both)• Standard Care (Cl)• Exposure to intervention (Tx)
3 months	
• Standard Care (Cl)• Exposure to intervention (Tx)• Follow-up assessment (Both)
6 months	
• Standard Care (Cl)• Exposure to intervention (Tx)• Follow-up assessment (Both)• In-depth interviews with PWH begin (Both)
9 months	
• Follow up assessment (Both)
Study end	
• Follow-up interviews for interventionists (5 per site)• In-depth interviews with key stakeholders (15 per site)

or via a HIPAA compliant platform such as Skype or Zoom. During virtual enrollment visits, the RA will complete informed consent electronically through REDCap.

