D. Description, Risks and Justification of Procedures and Data Collection Tools

Description of data collection tools

D.1. Individual interviews to adapt infographics to the Colorado context.

Participants will initially complete a brief demographic questionnaire. Then, they will complete individual interviews with a study team member. Interviews will be audio recorded and later professionally transcribed.

D.2. RCT

D.2.1. Medical record review

Data will be extracted from medical records after each study visit and will include the primary outcome CD4 count as well as most recent viral load and currently prescribed ART regimen.

D.2.2. Baseline assessments

Baseline assessment will be administered either virtually or in-person at baseline visits and will collect demographics (age, length of time living with HIV, sex, gender, income, level of education among others), assess health literacy levels with two validated assessments, the Short Assessment of Health Literacy - Spanish & English (SAHL S&E)⁶⁵ and the Newest Vital Sign (NVS),⁶⁶ include a measure of acculturation, the Short Acculturation Scale for Hispanics (SASH),⁶⁷ and all other outcome measures not extracted from medical records (Table 1).

D.2.3. Follow up assessments

Follow up assessments will be administered either virtually or in-person at 3-, 6-, and 9-month visits and will include outcome measures (Table 1) and open-ended questions exploring infographic usability, satisfaction with infographic design, and recommendations for improvement. Questions regarding interventionists' communication strategies and intervention delivery will be included to further assess intervention fidelity and enable assessment of providers' communication variability.

D.2.4. Semi-structured in-depth interviews

In depth interviews with patient participants at the CO site will be conducted using a rigorously developed iterative interview guide.⁶³ Interviews at the CO site will include questions and probes to generate an explanatory model of participants' experience living with HIV and communicating about it in a clinical setting,⁶⁸ this data was already collected from participants in the DR and NY in preliminary studies. Questions to obtain feedback on how to adapt infographics and clinical communication will be included for all participants. Interviews will be audio recorded and later transcribed.

D.2.5. Follow up interviews with interventionists

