Transcripts from key stakeholders at each site will be analyzed using directed content analysis to identify implementation factors regarding the SMART app's integration with EHRs.⁷⁷⁻⁸⁰ Key considerations to enhance perceived usefulness and ease of use will be identified and incorporated into the final app.

D.9.5. Exploratory Aim 4: Conduct in-depth interviews with PWH in CO to explore their perceptions of HIV infection and preferences for health communication. Qualitative findings will be integrated with those from the NY and DR cohorts to detail variations and similarities, and identify areas for intervention refinement. To deeply and rigorously explore participants' perceptions of HIV infection and how they influence clinical communication, explanatory models of HIV infection among PWH at each site will be generated.^{68,81-83} Directed content analysis guided by McGuire's Classic Input-Output Framework for Constructing Persuasive Messages will be used to analyze transcripts from in-depth interviews.⁸⁴ Gioia's methodology will be followed to enhance qualitative rigor.⁸⁵ Results from each cohort (DR, CO, and NY) will be synthesized and integrated to establish variations and similarities in the HIV experience among distinct Latino cultures as well as establish how their unique perspectives shape intervention design and delivery.

Usability testing of Creole version of the app

Changes to the app will be made directly on the paper copies provided during the group. The scores of the SUS will be calculated according to the instrument guidelines.

Validation of infographics with non-Latino PWH

Quantitative data from the questionnaire that will be administered during interviews will be scored and descriptive statistics calculated. Audio recordings will be transcribed and analyzed for patterns. Representative quotes will be extracted.

E. Summarize Knowledge to be Gained

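### Exploratory Aim 4 pools treated and control Colorado patients into one explanatory model, so differences from the DR and NY cohorts may partly reflect infographic exposure rather than culture

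*Combined protocol and SAP*

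**What the plan says.** Section IV.C (Study Design) defines the Aim 4 component as "In-depth interviews with patient participants from the RCT (Aim 4". Table 2 places the start at the 6-month visit, in both arms: "In-depth interviews with PWH begin (Both". The same table schedules treated patients for the intervention at baseline, 3 and 6 months, and controls for standard care only.

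Section IV.D.2.4 asks the explanatory-model questions in CO alone, because "this data was already collected from participants in the DR and NY in preliminary studies". It does not name those studies. Section III describes several candidates: dissertation work in the DR, later work to develop the infographics, and one feasibility study each in the DR and NY. On the last two it says: "Another main limitation of both feasibility studies is that there was not a control group".

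Section IV.F, D.9.5 generates explanatory models by site. The three cohorts' results are then to be "synthesized and integrated to establish variations and similarities in the HIV experience among distinct Latino cultures", and the findings are to inform how the intervention is designed and delivered. The section describes no coding by arm, no record of infographic exposure, and no limit on how comparable the cohorts are.

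**The concern.** The intervention is meant to act on what these interviews explore. The infographics are described as "culturally appropriate and visually appealing representations of key HIV-related concepts". Table 1 lists information recall and engagement with the clinician as proximal outcomes, and Section III reports improved HIV-related knowledge and engagement in the uncontrolled DR feasibility study. Treated patients also see clinicians trained in motivational interviewing, while controls see other providers. On the protocol's own rationale, the two CO arms may describe HIV, and how they prefer to talk about it, differently.

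A pooled CO model hides any such difference. If the DR and NY interviewees had a different mix of exposure, a theme could separate CO from the other cohorts because of the intervention and be reported as cultural. The stake is the credibility of Aim 4's own comparison and of the refinements drawn from it.

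**Working it through.** Aim 4 has no stated sample size, power or test to reproduce. The check is a side-by-side reading plus a simple mixture argument.

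**Inputs**

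- CO interviewees: trial patients in both arms, from month 6 (Study Design; Table 2).
- Scheduled exposure at interview: two sessions if a treated patient is interviewed before the 6-month session, three if after; none for controls (Table 2).
- CO allocation: 41 treated and 41 control, from "n=164, 82 at each site, 41 per group" (Section IV.F, sample size).
- CO interviewees by arm: not stated. Mirroring the allocation is an assumption, giving 41/82 = 50% exposed.
- DR and NY share exposed at interview: not stated, so varied from 0% to 100%.

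**Exposure gap**

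Gap = CO share exposed - DR/NY share exposed.

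| DR/NY share exposed (assumed) | Gap, percentage points |
|---|---|
| 0% | 50 - 0 = +50 |
| 25% | 50 - 25 = +25 |
| 50% | 50 - 50 = 0 |
| 75% | 50 - 75 = -25 |
| 100% | 50 - 100 = -50 |

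The 0% row fits interviews held before the infographics were used. The 100% row fits interviews held after use in an uncontrolled study. Intermediate rows need interviews pooled from before and after exposure. DR and NY need not share the same row.

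**What a gap does to a theme**

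Suppose a theme is voiced by a fraction t of exposed and c of unexposed patients, identically in every culture. The pooled CO versus DR/NY difference is then gap × (t - c). At a gap of +50 or -50 points, half of the exposure effect would appear as a difference between cohorts, in either direction. At a gap of zero none would. The documents give neither t - c nor the gap.

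**Why coding by arm helps whatever the DR/NY exposure was**

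Let s be the DR/NY share exposed, and keep the assumption of no cultural difference. Then:

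- CO treated minus DR/NY = t - [s·t + (1 - s)·c] = (1 - s)(t - c)
- CO control minus DR/NY = c - [s·t + (1 - s)·c] = -s(t - c)

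These have opposite signs, or one is zero. Exposure alone therefore cannot produce a difference in the same direction in both CO arms. The argument assumes that controls were unexposed and treated patients exposed. Section IV.E (Potential Scientific Problems) anticipates departures from both, so sessions actually received should be recorded as well as arm.

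**The case against.** The case on the other side has real force.

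- A reader might infer that the plan treats the cohorts as differing only by culture. No section says so. D.9.5 speaks of variations and similarities, and plans no test or effect estimate.
- A reader might also infer that confounding is established and that half the CO sample is mismatched. The documents do not support this. Pooling arms distorts the comparison only if the DR/NY exposure share differs from CO's. Neither that share nor the arm split of the CO interviewees is given, and the absence of a control group in the feasibility studies does not show which study supplied the interviews or when they took place.
- Interviewing both arms is defensible. Aim 4 also seeks refinements to the intervention, for which patients who have used the infographics are useful informants. Adaptation for patients of Mexican descent is done separately, before the trial, under Aim 1.
- Arm is randomised and known in CO, so nothing is lost beyond recovery.
- Matching on exposure would not isolate culture. Section IV.B describes the CO clinic's Latino patients as 85% male and 90% Mexican, and the DR clinic's as 57% female and 81% Dominican. Country, care setting and data-collection period differ too. Section III says the NY patients are mainly of Dominican origin, so DR versus NY is not plainly a contrast of two cultures.

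All of this stands, and it limits the point to a possible distortion in an exploratory aim. It does not remove the point: D.9.5 still specifies a single model per site and a cultural reading of differences, with no step that would reveal an exposure effect. That separation by arm is possible makes the remedy cheap; the plan does not say it will be done.

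**Conclusion.** The point holds as a minor one. CO versus DR/NY differences in Aim 4 may partly reflect exposure to the intervention, and the plan has no step to detect this. The size and direction cannot be determined from the documents. The range of -50 to +50 points rests on two assumptions: that CO interviewees mirror the 1:1 allocation, and that DR/NY exposure could lie anywhere from none to all.

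A reader might go on to doubt the randomised comparison of CD4 count. Nothing here bears on it: the point concerns only how interview transcripts are compared across cohorts.

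**What to change.** In D.2.4 and D.9.5:

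1. Tag each CO transcript with randomised arm and number of infographic sessions received by the interview date, including any known exposure of a control.
2. Code the CO explanatory model separately by arm before the cross-cohort synthesis.
3. State which preliminary studies supplied the DR and NY interviews, when they were held, and whether interviewees had seen infographics.
4. Attribute a cross-cohort difference to culture only if the theme appears in both CO arms, or in the CO arm whose exposure matches DR/NY where that is known. Report themes confined to one arm separately, as possible effects of the intervention as delivered (infographics plus trained clinicians).
5. State that sex mix, country and care setting, and data-collection period differ between cohorts, and that NY and DR are both mainly Dominican, so culture is not isolated even after step 4.

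The cost is some wording and a coding variable. The downside is fewer CO transcripts behind each arm-specific comparison; if interviews are still to be held, choosing interviewees purposively by arm would limit this. The coding can also be done after the interviews are complete, because allocation is known.
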